8.2 Duration of response

For purposes of this study, response rate will be calculated based on the treated lobe only.

Overall response: The duration of overall response is measured from the time measurement

Copyright© 2015 Fox Chase Cancer Center® Clinical Trials Operations. All rights reserved. Version Date 02/27/2017

criteria are met for CR or PR (whichever is first recorded) until the first date that recurrent or progressive disease is objectively documented (taking as reference for progressive disease the smallest measurements recorded since the treatment started). The duration of overall CR is measured from the time measurement criteria are first met for CR until the first date that recurrent disease is objectively documented.

Stable Disease: Stable disease is measured from the start of the treatment until the criteria for progression are met, taking as reference the smallest measurements recorded since the treatment started.

8.3 Time to progression

Time to progression (TTP) is defined as the duration of time from start of treatment to progression in the treated lobe.

9.0 Statistical Considerations:

The study is a phase I study with a total of 3 dose levels. For the dose-escalation portion of the study, approximately 9 evaluable subjects will be required if DLTs do not occur (3 subjects in each of the dose cohorts, 50, 75, 100). If a DLT does occur among the first 3 subjects in a cohort, 3 additional subjects will be added to the cohort. In case 2 or more DLTs occur in a cohort, a total of 6 subjects will be treated at the preceding dose, which will be evaluated for MTD. At a minimum we will enroll 3 patients at each dose level with an expansion of the last dose level with 14 additional patients. Therefore we are estimating accrual of 9-30 patients under this protocol. For each dose-escalation arm during Phase 1 the evaluable population for DLT includes all subjects enrolled in the dose-escalation arm, who received at least 1 full cycle of DEBIRI. The Safety Population includes all subjects who receive treatment with DEBIRI.

At the dose expansion level 10% of DLT will be acceptable and 33% will be unacceptable. We would terminate the study if ever 4 DLTs occur including 1 that would have occurred in the MTD cohort of 6 patients. The chance of declaring the treatment too toxic when only 10% toxic is about 9% while the chance of this decision when the true toxicity is 33% is about 85%.

Reporting and Exclusions

9.1.1 Evaluation of toxicity.

All patients will be evaluable for toxicity from the time of their first treatment with DEBIRI until study completion. Toxicity reports will be carried out as detailed in section 5.0.

9.1.2 Evaluation of response.

All patients with measurable disease included in the study will be assessed for response to treatment, even if there are major protocol treatment deviations or if they are ineligible. Each patient will be assigned one of the following categories:

- 1) Complete response, 2) partial response, 3) stable disease, 4) progressive disease, 5) early death from malignant disease, 6) early death from toxicity, 7) early death because of other cause, or 8) unknown (not assessable, insufficient data). (47)

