4.3 Definition of Dose-Limiting Toxicities

Definition: This will be defined as any of the following toxicities occurring during the 3 weeks following each DEBIRI treatment that are judged as possibly, probably, or definitely related to study agent:

- \geq Grade 3 non-hematologic toxicity (excluding nausea, vomiting, or diarrhea responding to symptomatic management or LFTs)

- \geq Grade 3 nausea, vomiting and diarrhea that has not responded to maximal medical symptomatic management after \geq 72hr will be considered a DLT
- Grade 3 thrombocytopenia lasting > 5 days
- Grade 3 thrombocytopenia with \geq grade 3 bleeding at any site
- Grade 4 thrombocytopenia
- Grade 4 neutropenia lasting > 5 days or associated with fever or infection
- Grade 3 alkaline phosphatase increase lasting more than 2 weeks post procedure
- Grade 4 alkaline phosphatase at any time
- Grade 3 ALT, AST and/or bilirubin elevation will be classified as a DLT based on the following criteria:
 - persistent AST/ALT elevation of 5-10 times the upper limit of normal for more than 2 weeks
 - Persistent AST/ALT elevation of $>10-20$ times the upper limit of normal for more than 1 week
- Grade 4 ALT, AST and/or bilirubin elevation at any time.

Dose escalation will proceed to the next cohort according to the following schema:

# of Patients with DLT at a Given Dose	Escalation Decision Rule
0 out of 3	Enter 3 patients at the next dose level.
≥ 2	Dose escalation will be stopped. This dose level will be declared to have exceeded the maximum tolerated dose. Three additional patients will be entered at the next lowest dose level if only 3 patients were treated previously at that dose.
1 out of 3	Enter at least 3 more patients at this dose level. 
 • If 0 of these 3 patients experience DLT, proceed to the next dose level. • If 1 or more of this group suffer DLT, then dose escalation is stopped, and this dose is declared to have exceeded the maximum tolerated dose. Three additional patients will be entered at the next lowest dose level if only 3 patients were treated previously at that dose.
≤ 1 out of 6	This is generally the MTD and recommended phase 2 dose. At least 6 patients must be entered at the recommended phase 2 dose.

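### Section 9.0 sizes the no-DLT path at 100 mg as 3 patients plus 14, but its 4-DLT stopping rule and the 9%/85% assume 6 patients with at most 1 DLT before the 14

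*Combined protocol and SAP*

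**What the plan says.** Section 9.0 sizes escalation as "approximately 9 evaluable subjects will be required if DLTs do not occur (3 subjects in each of the dose cohorts, 50, 75, 100"). It enlarges a cohort to 6 in two situations. One is a DLT in the first three: "If a DLT does occur among the first 3 subjects in a cohort, 3 additional subjects will be added to the cohort". The other is a step back after 2 or more DLTs, when "a total of 6 subjects will be treated at the preceding dose, which will be evaluated for MTD". It then sets the minimum enrolment and the expansion: "At a minimum we will enroll 3 patients at each dose level with an expansion of the last dose level with 14 additional patients". Accrual follows: "Therefore we are estimating accrual of 9-30 patients under this protocol".

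The next paragraph of Section 9.0 takes 10% as an acceptable DLT rate and 33% as unacceptable, and gives the rule: "We would terminate the study if ever 4 DLTs occur including 1 that would have occurred in the MTD cohort of 6 patients". It states that the chance of declaring the treatment too toxic is about 9% at the first rate and about 85% at the second.

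In the Section 4.3 table, the instruction after 0 of 3 is "Enter 3 patients at the next dose level". The last row treats at most 1 DLT in 6 as generally defining the MTD, and adds: "At least 6 patients must be entered at the recommended phase 2 dose". The schema and Section 1.5 place the expansion at the MTD.

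**The concern.** The two paragraphs of Section 9.0 describe different designs for 100 mg when none of its first 3 patients has a DLT. The first leads to 3 + 14 = 17 patients there. The second calculates for 6 + 14 = 20. Section 4.3 does not close the gap, because 100 mg is Level 3 of 3 and there is no next level to enter.

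This is not a rare branch. Of the ways 100 mg can clear escalation, 0 of 3 accounts for 80% at a 10% DLT rate and 69% at 33%.

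At stake is the only quantitative toxicity boundary in the expansion, in a trial whose sole primary objective is the MTD. With three fewer patients observed, the rule is less likely to stop a dose that the protocol itself calls unacceptable, and the stated 85% would no longer describe it.

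**Working it through.** **Inputs.** DLT rates p = 10% and 33%, expansion of 14, stop at 4 DLTs in total including any in the MTD cohort (all Section 9.0); MTD criterion of at most 1 in 6 and the 3+3 rules (Section 4.3). DLTs are treated as independent binomial events. X14 is the number of DLTs among the 14. Results are given as 10% / 33%.

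**Building blocks**
- P(X14 ≥ 4) = 0.0441 / 0.7301 (needed when no DLT came before the 14)
- P(X14 ≥ 3) = 0.1584 / 0.8899 (needed when one DLT came before)
- P(0 of 6) = 0.5314 / 0.0905; P(1 of 6) = 0.3543 / 0.2673
- P(0 of 3) = 0.7290 / 0.3008; P(1 of 3) = 0.2430 / 0.4444
- P(1 of 3, then 0 of 3) = 0.1771 / 0.1337

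**1. The plan's own figures.** Given at most 1 DLT in 6, then 14:

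[P(0 of 6) × P(X14 ≥ 4) + P(1 of 6) × P(X14 ≥ 3)] / P(≤ 1 of 6)

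- 10%: (0.5314 × 0.0441 + 0.3543 × 0.1584) / 0.8857 = 8.98%
- 33%: (0.0905 × 0.7301 + 0.2673 × 0.8899) / 0.3578 = 84.95%

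These are the stated 9% and 85%. Counting at least 4 DLTs in 20 patients without the condition gives 13.3% / 93.6%, which does not match.

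**2. Section 9.0 taken literally.** 100 mg clears with 0 of 3 (then 14) or with 1 of 3 followed by 0 of 3 (then 14):

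[P(0 of 3) × P(X14 ≥ 4) + P(1 of 3, then 0 of 3) × P(X14 ≥ 3)] / [P(0 of 3) + P(1 of 3, then 0 of 3)]

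- 10%: (0.7290 × 0.0441 + 0.1771 × 0.1584) / 0.9061 = 6.6%
- 33%: (0.3008 × 0.7301 + 0.1337 × 0.8899) / 0.4344 = 77.9%

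This is the like-for-like comparison with step 1: both are chances that the 4-DLT rule stops the expansion, given that 100 mg has cleared.

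**3. The 0-of-3 branch alone**
- 3 + 14: P(X14 ≥ 4) = 4.4% / 73.0%
- Three more first, with at most 1 DLT in the six, then 14: [P(0 of 3) × P(X14 ≥ 4) + P(1 of 3) × P(X14 ≥ 3)] / [P(0 of 3) + P(1 of 3)] = 7.3% / 82.5%

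**4. A true 33% rate at 100 mg, counting stops in the escalation cohort too.** The chance that neither escalation nor the rule stops it:
- 3 + 14: 0.3008 × (1 − 0.7301) + 0.1337 × (1 − 0.8899) = 0.0812 + 0.0147 = 9.6%
- Six first: 0.0905 × (1 − 0.7301) + 0.2673 × (1 − 0.8899) = 0.0244 + 0.0294 = 5.4%

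**5. Accrual with no DLT in escalation.** 9 + 14 = 23 with three at 100 mg; 12 + 14 = 26 with six. Both lie within 9-30, so the accrual range does not show which is meant.

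**The case against.** The strongest reply is that the documents, read together, already mean six first. The expansion is at the MTD, the only row of Section 4.3 that identifies an MTD needs at most 1 DLT in 6, at least 6 must be entered at the recommended dose, and the stopping rule names a cohort of 6. The 3 per level in Section 9.0 is worded as a minimum and the 9 as approximate. This stands as the likely intent, and the stated 9%/85% are correct for that design. It does not remove the gap. Section 9.0 gives 3 at 100 mg for exactly the no-DLT case and does not count the three patients needed to reach six. The minimum of 6 in Section 4.3 is not stated as a condition for opening the expansion, so the first 3 of the 14 could be taken to satisfy it.

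A second reply concerns size, and it is right. A reader might infer from step 3 that the stated figures fall to 4.4%/73.0%, or that a 33% rate is missed 27% of the time. The documents do not support either. Those figures hold only given no DLT before the 14, and 0 of 6 followed by 14 gives the same 4.4%/73.0%. At a 33% rate, 0 of 3 itself has a probability of only 30%. The fair comparisons are those in steps 2 and 4.

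**Conclusion.** The concern holds as an internal inconsistency of moderate size. Followed literally, Section 9.0 gives its stopping rule 6.6%/77.9% instead of the stated 9%/85%: about 7 percentage points less chance of stopping at a 33% DLT rate, once 100 mg has cleared. Over escalation and expansion together, the chance of missing a 33% rate at 100 mg is about 4 points higher (9.6% against 5.4%).

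This rests on independent DLTs with a constant rate, on the 14 being added directly after 0 of 3, and on the 4-DLT rule being applied unchanged to 17 patients. It does not show that the sponsor intended 3 + 14; Section 4.3 points the other way. Nor is the 9%/85% calculation itself wrong. The inconsistency affects only 0 of 3 at 100 mg: a lower dose reached by stepping back is filled to 6 under both sections.

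**What to change.** State in Section 9.0, and in a Level 3 line of the Section 4.3 table, that if 0 of 3 patients at 100 mg have a DLT, 3 more are treated at 100 mg, and that the 14-patient expansion opens at the MTD only after 6 patients there with at most 1 DLT. Every route to clearing 100 mg is then at most 1 DLT in 6, so the 4-DLT rule and the 9%/85% stand as written. Change the no-DLT escalation count in Section 9.0 from 9 to 12.

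The cost is three patients, only after 0 of 3 at 100 mg: 26 instead of 23 if escalation has no DLTs. If both lower cohorts were also enlarged, the total would be 6 + 6 + 6 + 14 = 32, just over the estimated 30. The present text already reaches 32 when each level has 1 DLT in its first three and none in the next three, so the upper accrual figure is worth correcting at the same time.

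If only 3 patients are wanted at 100 mg before the expansion, say so, drop the reference to a cohort of 6 on that path, and restate the operating characteristics as about 7% and 78%. That costs no patients but accepts the weaker boundary.

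### Section 9.0 defines the escalation DLT-evaluable set by exposure alone and leaves 'cycle' undefined, so on two of three readings a treated patient with a DLT can fall out of the count that sets the MTD

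*Combined protocol and SAP*

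**What the plan says.** Section 9.0 sets two populations in consecutive sentences. For each escalation arm, "the evaluable population for DLT includes all subjects enrolled in the dose-escalation arm, who received at least 1 full cycle of DEBIRI". The Safety Population is everyone treated with DEBIRI.

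The same section gives the planned number as "approximately 9 evaluable subjects will be required if DLTs do not occur", split as three per dose. It then gives the cohort rules: "If a DLT does occur among the first 3 subjects in a cohort, 3 additional subjects will be added to the cohort", and "In case 2 or more DLTs occur in a cohort", the preceding dose is filled to six and evaluated as the MTD. The expansion rule follows: "We would terminate the study if ever 4 DLTs occur including 1 that would have occurred in the MTD cohort of 6 patients".

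Section 4.3 defines a DLT as "any of the following toxicities occurring during the 3 weeks following each DEBIRI treatment" and judged at least possibly related. Its decision table counts patients with a DLT at a dose and does not mention evaluability. Section 9.1.1 adds: "All patients will be evaluable for toxicity from the time of their first treatment with DEBIRI until study completion".

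The treatment plan (4.1.1, 4.1.2) is written in treatments: two per lobe, three weeks apart. The text available for this review, which lacks part of the section 1.4 background, does not define a DEBIRI cycle. The only other cycles mentioned are of FOLFOX, in the background.

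**The concern.** An exposure-only definition is safe when a DLT cannot stop a patient from reaching the required exposure. Here it may.

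DLTs are scored after each treatment, so one can follow treatment 1. Section 4.0 requires recovery before retreatment, section 4.1.2 removes patients whose laboratory values do not recover in time, and sections 4.6 and 4.6.1 allow therapy to end for toxicity. Separately, section 4.2 accepts that the intended dose may not be fully delivered.

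The number of patients with a DLT decides escalation and the MTD, which is the only primary objective. A dropped DLT biases in one direction, toward escalation. For example, two DLTs in three patients stop escalation under 4.3. If one of the two is ruled not evaluable and replaced by a DLT-free patient, the count is one of three and the cohort is expanded instead. Two analysts following the text could therefore reach different decisions from the same patients.

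**Working it through.** **1. What the sentence does under each reading**

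- *Cycle = one treatment of any amount.* Every treated patient qualifies. Nothing is lost.
- *Cycle = the planned pair.* A patient whose DLT after treatment 1 prevents treatment 2 does not qualify. A patient who recovers and is retreated does.
- *Full = full dose.* A patient with incomplete delivery and a DLT does not qualify. The rate is biased only if short delivery and DLT are linked. The documents give nothing from which to size this.

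**2. The plan's own figures**

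Inputs from 9.0: MTD cohort of 6, expansion of 14, stop at 4 DLTs in total, true rates 10% and 33%. Let b(n,k) be the binomial probability and X the DLTs among the 14. Given at most 1 DLT in the six:

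P(stop) = [b(6,0)·P(X≥4) + b(6,1)·P(X≥3)] / [b(6,0) + b(6,1)]

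- At 10%: (0.5314×0.0441 + 0.3543×0.1584) / 0.8857 = 0.0898. The plan says about 9%.
- At 33%: (0.0905×0.7301 + 0.2673×0.8899) / 0.3578 = 0.8495. The plan says about 85%.

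Both reproduce with every DLT counted.

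**3. Full counting at a true 33%**

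- Pass a 3+3 level: (1−p)³ + 3p(1−p)⁵ = 0.3008 + 0.1337 = 0.434.
- At most 1 of 6: (1−p)⁶ + 6p(1−p)⁵ = 0.0905 + 0.2673 = 0.358.
- Accepted and surviving the expansion: 0.0905×P(X≤3) + 0.2673×P(X≤2) = 0.0905×0.2699 + 0.2673×0.1101 = 0.054.

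**4. Pair reading only**

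Assumptions, none given in the documents:

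- f = share of DLTs arising after treatment 1 (25-75%).
- g = share of those patients not retreated (half or all).
- Dropped patients are replaced.
- The expansion counts every DLT.

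The counted rate is pc = p(1−fg)/(1−pfg). It replaces p in the formulas for the six and for the 3+3 level; the 14 keep p = 0.33.

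| f, g | pc | Pass level | At most 1 of 6 | Accepted and surviving | P(stop), given accepted |
|---|---|---|---|---|---|
| full counting | 0.330 | 0.434 | 0.358 | 0.054 | 0.850 |
| 0.25, 0.5 | 0.301 | 0.492 | 0.418 | 0.065 | 0.845 |
| 0.50, 0.5 or 0.25, 1 | 0.270 | 0.557 | 0.488 | 0.078 | 0.840 |
| 0.75, 0.5 | 0.235 | 0.632 | 0.569 | 0.095 | 0.834 |
| 0.50, 1 | 0.198 | 0.714 | 0.661 | 0.115 | 0.825 |
| 0.75, 1 | 0.110 | 0.890 | 0.866 | 0.175 | 0.798 |

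At a true 10% the chance of passing a level moves from 0.906 to 0.924-0.992. With g = 0, nothing changes.

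**The case against.** The strongest reply is that a cycle means one treatment. Treatments are three weeks apart and DLTs are scored over three weeks after each, which is how a cycle is usually laid out. The criterion asks for at least one cycle *received*. If a cycle were the pair, a patient with unilobar disease would have only one planned, and 'at least' would do little work. On this reading a patient with a DLT after treatment 1 is counted. This stands as a plausible reading, but the text does not settle it. The section 7.0 calendar is a repeatable block of two treatments. A DLT set that equals everyone treated would also make the separate Safety Population redundant in escalation. And the word 'full' still leaves incomplete delivery open.

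A reader might infer several stronger things that the documents do not support:

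- *That the plan excludes patients with DLTs.* No sentence does; the gap is the absence of a clause that keeps them.
- *That 9.0 contradicts itself.* Its opening sentence splits the evaluable nine into three per cohort, and the later cohort counts can be read as continuing that usage.
- *That 9.1.1 conflicts with the definition.* It concerns toxicity in general and fits the Safety Population. The clear mismatch is with the 4.3 table.
- *That the 9% and 85% are wrong.* They are right when every DLT counts.
- *That a DLT ends treatment.* Section 4.0 allows retreatment after recovery, and 4.6.1 says only that patients may be withdrawn. The 89% therefore needs three quarters of DLTs after treatment 1 and none of those patients retreated.

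**Conclusion.** The wording gap is certain; the size of any bias is not. The DLT-evaluable set for escalation rests on an undefined unit of exposure, and on two of three readings it can lose the patients whose DLTs matter most to the decision.

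Under the pair reading and the assumptions above, the chance of passing a level at a true 33% rises from 43% to 49-89%, and of at most 1 DLT in six from 36% to 42-87%. The expansion rule absorbs most of this if it counts every DLT: acceptance plus survival goes from 5% to 6-18%, and the 85% becomes 80-85%. That limits the final error, but patients would by then have been entered at a higher level. There is no effect if a cycle is one treatment of any amount, if all affected patients are retreated, or if DLTs are counted regardless. This should be fixed because it bears on the primary objective and the repair is cheap.

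**What to change.** In 9.0, define 'cycle' and add: *any patient who received any DEBIRI and had a DLT is DLT-evaluable and is never excluded or replaced.* Use the same definition in the 4.3 table and for the MTD-cohort count carried into the expansion stopping rule. Report DLTs among all treated patients beside the evaluable count.

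The cost is one definition and a matching line in 4.3. Keeping patients with DLTs requires no extra accrual, and the stated 9% and 85% stay as they are.

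Three neighbouring matters are separate, and the study team should decide or reconcile them:

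- Whether DLT-free patients who leave early are replaced. This is a design choice and does add patients.
- Which treatments form the DLT window, including treatments 3 and 4 in bilobar disease.
- The retreatment laboratory limits, which differ between 4.0 (AST/ALT and alkaline phosphatase below 2.5 × ULN) and 4.1.2, which refers back to 3.1.11 (at most 2 × ULN).

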9.2 Data Safety Monitoring Plan

9.2.1 Monitoring Plan

FCCC ISRU will monitor the medical and study records of each participant accrued throughout the course of the study. In addition, the ISRU will collect and report data to the study Sponsor-Investigator who will review these data on a regular basis at a rate dependent on subject accrual. All serious adverse events (SAEs) will be reviewed on a real time basis first by the study site PI and subsequently by the ISRU and Sponsor-Investigator as applicable.

9.2.2 Data & Safety Monitoring Committee

Interim analysis of toxicity, outcome and ongoing scientific investigations may be performed at least every 6 months by the Fox Chase Cancer Center Data Safety Monitoring Board (FCCC DSMB). In this capacity the FCCC DSMB will serve as an advisory committee to the Sponsor-Investigator. The FCCC DSMB will review those aspects of this trial that are outlined in the responsibilities section of the Data and Safety Monitoring Plan (DSMP). If the committee decides that changes should be made to this trial, it will make recommendations in writing to the Study Sponsor-Investigator, the Associate Director of Clinical Research, and the Protocol Management Executive Committee, which, in turn, have the authority to approve or disapprove these recommendations. These changes will be discussed with the Study Sponsor-Investigator before they are implemented. These changes may include early termination of accrual. Other changes might include altering the accrual goals or changing the eligibility criteria for the trial.

10.0 Administrative

This study will be conducted in accordance with local, state and Federal regulations and according to accepted good clinical practice guidelines.

10.1 Data Reporting

The FCCC Study Monitor will request case report forms to be completed within 2 weeks of the protocol visit. Participating sites are responsible to respond to queries prior to the next scheduled monitoring visit.

The ISRU is responsible for compiling and submitting data to the Sponsor-Investigator and statistician on an ongoing basis for monitoring as described in the data safety monitoring plan and reporting to the Data and Safety Monitoring Board.

All patient information will be stored in an EDC system accessible only to the study team members for the purpose of entering, reviewing and analyzing data. Any paper records, such as case report files, produced will be stored in a secure location.

The ISRU is responsible for distributing and tracking review of all IND/IDE Action Letters, Safety Reports, study specific Serious Adverse Events

